10.1.1 Follow-up of Adverse Events

All AEs that are ongoing at the end of the patient's participation in the trial will be followed-up until the event is resolved or reaches a satisfactory outcome as deemed by the Investigator. Follow-up actions for all serious adverse events (SAEs) will be performed according to appropriate clinical care practices and may depend on the nature of the event. These will be determined after internal review and/or Sponsor review. The follow-up information should only include new (updated and/or additional) information that reflects the situation at the time of the Investigator's signature.

Follow-up information on (S)AEs will be updated using the (S)AE Form. If a non-serious event becomes serious during the follow-up, the AE Form and SAE Form must be used and reporting timelines follow those of an SAE.

The Investigator must forward follow-up information on SAEs, and if previously non-serious AEs become SAEs, to the Sponsor.

10.1.2 Precautions

Normal precautions taken for a human trial will be taken during this trial. Qualified and well-trained physicians and medical staff will instruct the patients. During a patient's participation in the trial, the Investigator should ensure that adequate medical care is provided to the patient for any AEs, including clinically significant laboratory values related to the trial. The Investigator should inform the patient when medical care is needed for intercurrent illnesses of which the Investigator becomes aware.

For further information on safety precautions for ZP4207, Lilly glucagon, Lilly Humalog, and the iLet, please refer to the current version of the Investigator's Brochure (IB) for ZP4207

Clinical Trial Protocol
ZP4207-16051

Version number: 3.0
Amendment 2.0
Date: 03 August 2016

(Zealand Pharma A/S, 2015, or any updates hereof), and the SPC for Glucagon (Eli Lilly, 2012) and Humalog (Eli Lilly, 2015), respectively.

10.1.3 **Assessment of Adverse Events by the Investigator**

Intensity of an Adverse Event

The maximum intensity (severity) of all AEs must be assessed by the Investigator and documented. Severity should be graded when the AE outcome is known:

- **Mild:** A type of AE that is usually transient and may require only minimal treatment or therapeutic intervention. The event does not generally interfere with usual activities of daily living.
- **Moderate:** A type of AE that is usually alleviated with additional specific therapeutic intervention. The event interferes with usual activities of daily living, causing discomfort but poses no significant or permanent risk of harm to the patient.
- **Severe:** A type of AE that interrupts usual activities of daily living, or significantly affects clinical status, or may require intensive therapeutic intervention.

A “severe” reaction does not necessarily deem the AE as “serious,” and an SAE may not be “severe” in nature.

Causality Relationship to IMP

Insulin (insulin lispro, Lilly Humalog), glucagon (glucagon for injection, Eli Lilly), and ZP4207 are all regarded as IMP.

The causality of each AE should be assessed by the Investigator according to the following classification:

- **Related:** Good reason and sufficient documentation to assume a causal relationship.
- **Not related:** No relationship to trial product can be established.

Outcome of an Adverse Event

The outcome of all AEs must be assessed by the Investigator and documented by his/her staff. The following definitions should be used:

- **Recovered/resolved:** The patient has fully recovered, or by medical or surgical treatment the condition has returned to the level observed at the first trial-related activity from Visit 3.
- **Recovering/resolving:** The condition is improving and the patient is expected to recover from the event. This term is only applicable if the patient has completed the trial.
- **Recovered/resolved with sequelae:** The patient has recovered from the condition, but with lasting effect due to a disease, injury, treatment, or procedure. If a sequela meets an SAE criterion, the AE must be reported as an SAE.
- **Not recovered/not resolved:** The condition of the patient has not improved and the symptoms are unchanged, or the outcome is not known.
- **Fatal:** This term is only applicable if the patient died from a condition related to the reported AE. Outcomes of other reported AEs in a patient before he/she died should be assessed as “recovered/resolved,” “recovering/resolving,” “recovered/resolved with sequelae,” or “not recovered/not resolved.” An AE with a fatal outcome must be reported as an SAE.
- **Unknown:** This term is only applicable if the patient is lost to follow-up.

Clinical Trial Protocol
ZP4207-16051

Version number: 3.0
Amendment 2.0
Date: 03 August 2016

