4.4 Withdrawal Criteria

The participation of individual patients will be discontinued if they experience:

- Seizure or unconsciousness associated with hypoglycemia and associated with participation in the trial
- Persistent nausea and vomiting thought to be related to glucagon dosing associated with participation in the trial
- Hospitalization associated with participation in the trial
- Pregnancy
- Diabetic ketoacidosis

If more than 1 patient must be withdrawn from the trial for these reasons, the trial will stop and a vote of the Data and Safety Monitoring Board (DSMB) will be required to restart it. All AEs that are serious and unexpected but related will be reported to the DSMB within 5 working days.

Note that patients may discontinue participation at any time. Patients may be removed from the trial for other reasons, for instance, failure to comply with trial procedures or intercurrent illness that is unrelated to the BP but that precludes safe participation. Discontinuation of participation for these reasons will not contribute to a decision to discontinue the trial.

Clinical Trial Protocol
ZP4207-16051

Version number: 3.0
Amendment 2.0
Date: 03 August 2016

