10.2 Serious Adverse Events

An SAE is any untoward medical occurrence that at any dose:

- Results in death
- Is life-threatening
- Requires inpatient hospitalization or prolongation of existing hospitalization
- Results in persistent or significant disability or incapacity
- Is a congenital anomaly or birth defect
- Medically important

Medical judgement must be exercised in deciding whether an AE is believed to be “medically important.” Medically important events may not be immediately life-threatening or result in death or hospitalization, but may jeopardize the patient or may require intervention to prevent one of the other outcomes listed in the [definition](#) above.

Suspected Unexpected Serious Adverse Reactions (SUSAR)

A SUSAR is an AE fulfilling one of the criteria of seriousness and being assessed as related to an IMP, the nature or severity of which is not consistent with the applicable reference document (e.g., ZP4207 IB or package leaflet/SPC for an approved product).

Unanticipated Adverse Device Effect (UADE)

A UADE is any serious adverse effect on health or safety, any life-threatening problem or death caused by, or associated with a device, if that effect, problem, or death was not previously identified in nature, severity, or degree of incidence in the application; or any other unanticipated serious problem associated with a device that relates to the rights, safety, or welfare of patients.

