10.3 Adverse Event Reporting – Procedures for Investigators

The Principal Investigator and co-investigators will review any AEs and report any SAEs to the Sponsor as soon as possible and within 24 hours of obtaining knowledge of the event. The Principal Investigator and co-investigators will promptly report AEs to the Partner’s Institutional Review Board (IRB) and to the BU IRB (unless oversight is ceded by the BU IRB to the Partners IRB), in accordance with local requirements.

[name] is the Sponsor of the Investigational Device Exception for the BP and Zealand Pharma A/S is the Sponsor of the IND for ZP4207.

Reports of AEs will be submitted to the FDA in compliance with the terms of the Code of Federal Regulations.

All events meeting the definition of an AE must be collected and reported from the first trial-related activity from Visit 3 until the end of the post-treatment follow-up period. At each contact with the site (visit or telephone, excluding safety visits, where the patient is not seeing the Investigator or staff [e.g., visits to the laboratory], the patient must be asked about AEs. All AEs, either observed by the Investigator or reported by the patient, must be recorded by the Investigator and evaluated.

The Investigator should record the diagnosis, if possible. If no diagnosis can be made, the Investigator should record each sign and symptom as individual AEs.

Clinical Trial Protocol
ZP4207-16051

Version number: 3.0
Amendment 2.0
Date: 03 August 2016

All AEs must be recorded by the Investigator. One single AE Form must be used per AE from start to resolution. For SAEs, the SAE Form must also be completed.

AE information should include the following:

- Patient identification number on all pages
- Date and time of treatment start
- Date and time of onset and date of outcome
- Date and time of Investigator's first information on the (S)AE
- Seriousness
- Severity
- Causal relationship with IMP ZP4207
- Causal relationship with IMP insulin
- Causal relationship with IMP glucagon
- Causal relationship with medical device
- Causal relationship with procedures
- Interruption or withdrawal of treatment with IMP or medical device and other measures taken
- Outcome

All AEs are coded; details are described in the trial specific Data Management Plan.

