The Investigator must report initial information in writing on the SAE Form for all SAEs to the Sponsor's responsible pharmacovigilance unit (here: Lindeq) immediately (within 24 hours) after obtaining knowledge about the event.

Name: [REDACTED]
Company: Lindeq
Address: [name]
Tel: [REDACTED]
Fax: [REDACTED]
Mobile: [REDACTED]
E-mail: [contact]

In addition and meeting the same timeline, Investigators must report all SAEs to Zealand Pharma A/S by forwarding the SAE Form electronically within 24 hours of obtaining knowledge of the event to the representatives of Zealand Pharma A/S.

Names: [REDACTED] and [REDACTED]
Address: [name]
Tel: [REDACTED]
E-mails: [REDACTED]

It is the responsibility of Lindeq to report all SUSARs that occur in this trial to the Competent Authorities and to the Investigators. It is the responsibility of the Investigators to report the SUSARs to the IRBs in accordance with the local requirements in force and the International Conference on Harmonisation (ICH) guideline for Good Clinical Practice (GCP). The trial monitor must be informed accordingly.

Clinical Trial Protocol
ZP4207-16051

Version number: 3.0
Amendment 2.0
Date: 03 August 2016

It is the responsibility of Lindeq to report all serious adverse reactions on insulin lispro and glucagon for injection to the Eli Lilly Pharmacovigilance department within 5 days.

It is the responsibility of the Investigators to report all UADEs to Beta Bionics within 24 hours of the time they are detected. It is the responsibility of the Investigators to report all UADEs to the IRB in accordance with the local requirements in force and the ICH GCP. It is the responsibility of Beta Bionics to report all UADEs to the Competent Authorities.

All device deficiencies should be documented and should be reported to Beta Bionics within 24 hours. Device deficiencies are inadequacies of a medical device with respect to its identity, quality, durability, reliability, safety, or performance.

Name: [REDACTED]
Company: Beta Bionics, Inc.
Address: [name]
[name], United States
Tel: [REDACTED]
E-mail: [REDACTED]

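### The two-level causality scale in Section 10.1.3 sends plausible but under-documented events to *Not related*, so a serious, unexpected one misses SUSAR handling and the 5-working-day DSMB report

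*Protocol*

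**What the plan says.** Protocol Section 10.1.3 assigns the judgment to the investigator: "The causality of each AE should be assessed by the Investigator according to the following classification". The two classes are *Related*, defined as "Good reason and sufficient documentation to assume a causal relationship", and *Not related*, defined as "No relationship to trial product can be established". The same definitions stand in versions 1.0, 2.0 and 3.0.

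Two reporting duties depend on the label:

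- Section 10.2: "A SUSAR is an AE fulfilling one of the criteria of seriousness and being assessed as related to an IMP", with the further condition that the event is not consistent with the reference document. Section 10.3 then adds: "It is the responsibility of Lindeq to report all SUSARs that occur in this trial to the Competent Authorities and to the Investigators". The investigators pass SUSARs on to the IRBs.
- Section 4.4, repeated in Section 10.6.1: "All AEs that are serious and unexpected but related will be reported to the DSMB within 5 working days".

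Section 10.3 asks for five causality judgments on each AE: ZP4207, insulin, glucagon, procedures and the device ("Causal relationship with medical device"). The definitions in Section 10.1.3 stand under a heading about the IMP, and *Not related* is worded for the trial product only.

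**The concern.** The first definition sets two conditions, a good reason and enough documentation. The second takes whatever cannot be established. An event the investigator suspects but cannot document well therefore goes to *Not related* by default. A SUSAR is by name a suspected reaction, yet the scale that feeds it leaves no room for suspicion alone.

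This trial makes such events likely. ZP4207 or glucagon, iLet insulin, the patient's own pump at a raised basal rate (Section 7.4.1) and a first-generation device all act at once, so attribution will often be uncertain. What is at stake is whether a suspected serious reaction gets expedited handling in a trial whose primary objective is safety and tolerability.

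**Working it through.** No arithmetic applies: the protocol states no figure on this point. The check is to follow one event through every route in version 3.0. Take a serious, unexpected AE with a plausible link to an IMP but insufficient documentation, labelled *Not related* under Section 10.1.3.

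| Route | Section | Needs *Related*? | Outcome |
|---|---|---|---|
| SAE to sponsor and pharmacovigilance unit, 24 hours | 10.3 | No | Reached |
| SUSAR to authorities, investigators and IRBs | 10.2, 10.3 | Yes ("being assessed as related to an IMP") | Missed |
| DSMB, 5 working days | 4.4, 10.6.1 | Yes | Missed |
| DSMB told of serious, unexpected AEs, no deadline | 10.6.1 | No | Reached |
| Sponsor Safety Committee review of all AEs | 10.6.2 | No | Reached |
| UADE to device company, 24 hours | 10.2, 10.3 | No; its own test, which includes association with the device | Unaffected |

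Could the label be raised later? Section 10.1.3 names only the investigator. Section 10.1.1 mentions sponsor review, but for follow-up actions on SAEs, not for causality. The text at hand contains no sponsor causality assessment.

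Now take a non-serious AE with the same uncertainty. It cannot meet the SUSAR definition or the timed DSMB rule, since both require seriousness. Under Section 11.2.1, relationship is an item in the individual AE listing. The summary table, made only if more than 20 treatment-emergent AEs are registered, is by system organ class and treatment period. The primary endpoint in Section 8.1 counts AEs and records their type without a causality filter. So only the listed relationship changes.

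Two inconsistencies appear along the way:

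1. Section 10.6.1 has two DSMB rules. One covers every serious and unexpected AE and has no deadline; the other covers only those that are also related and has 5 working days. They differ in scope and timing.
2. The withdrawal criterion for persistent nausea and vomiting (Sections 4.4 and 7.4.5) rests on what is thought to be related to glucagon dosing, a lower standard than Section 10.1.3. An event could count toward the DSMB restart vote and still be recorded as *Not related*.

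**The case against.** The strongest reply is that little is lost. Every SAE reaches the sponsor and the pharmacovigilance unit within 24 hours whatever its label, the Safety Committee reviews all AEs, and the DSMB hears of any serious and unexpected AE. Section 10.3 also sends AEs to the IRBs under local requirements and to the FDA under federal regulations. All of this stands and limits the point. It does not restore SUSAR status or the DSMB deadline, and the protocol does not say what those outside requirements would add.

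A second reply is that the wording asks for documentation sufficient to assume a link, not to prove it, and that separate judgments by product mean no single cause has to be isolated. Timed dosing, glucose and VAS data will help too. This is fair: an investigator may read the scale generously. But then the label depends on the reader, and the plain text still puts the unresolved case under *Not related*.

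Three stronger readings are tempting, and the documents do not support them:

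- A reader might infer that these events never reach the DSMB. The untimed sentence in Section 10.6.1 says otherwise; they lose the deadline, not the notice.
- A reader might infer that the primary safety result is biased in favor of ZP4207 or the iLet. AE number and type are not filtered by causality, and nausea is also measured directly on an hourly VAS as its own component of the endpoint.
- A reader might infer that device effects go unreported. UADEs and device deficiencies have their own route, which does not use the Section 10.1.3 label.

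**Conclusion.** The point holds in limited form. As written, Section 10.1.3 classes a plausible but under-documented event as *Not related*, and a serious, unexpected one then misses two routes: SUSAR reporting and the 5-working-day DSMB report. Other notification continues. For non-serious AEs the effect is confined to the AE listing.

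The number of events affected cannot be estimated. The documents give no split between clear and uncertain causality, so it could be none, or every serious, unexpected event whose cause is uncertain. With 10 to 12 patients expected to be randomized (Section 11.2.4), the absolute number is probably small, but each such event would matter for safety handling.

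The conclusion assumes that the definitions are applied literally and that no form, charter or safety plan outside the text at hand adds a sponsor causality assessment. It is a stated rule that needs changing, not a detail left to the SAP.

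**What to change.** In Section 10.1.3:

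- Define *Related* as a reasonable possibility that the product, device or procedure caused or contributed to the event, with uncertain cases classed as related.
- Define *Not related* as another cause explaining the event, or timing that makes a link implausible.
- State that both definitions apply to each of the five causality judgments listed in Section 10.3, so that device and procedures are covered.

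In Section 10.6.1, and in the matching sentence of Section 4.4, reconcile the two DSMB rules into one with a single scope and a single deadline.

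The cost is a wording amendment and a change to the AE form instructions. Somewhat more AEs will be labelled related, and some serious ones will enter SUSAR assessment that would not do so now. No endpoint, sample size or analysis changes.

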10.2 Serious Adverse Events

An SAE is any untoward medical occurrence that at any dose:

- Results in death
- Is life-threatening
- Requires inpatient hospitalization or prolongation of existing hospitalization
- Results in persistent or significant disability or incapacity
- Is a congenital anomaly or birth defect
- Medically important

Medical judgement must be exercised in deciding whether an AE is believed to be “medically important.” Medically important events may not be immediately life-threatening or result in death or hospitalization, but may jeopardize the patient or may require intervention to prevent one of the other outcomes listed in the [definition](#) above.

Suspected Unexpected Serious Adverse Reactions (SUSAR)

A SUSAR is an AE fulfilling one of the criteria of seriousness and being assessed as related to an IMP, the nature or severity of which is not consistent with the applicable reference document (e.g., ZP4207 IB or package leaflet/SPC for an approved product).

Unanticipated Adverse Device Effect (UADE)

A UADE is any serious adverse effect on health or safety, any life-threatening problem or death caused by, or associated with a device, if that effect, problem, or death was not previously identified in nature, severity, or degree of incidence in the application; or any other unanticipated serious problem associated with a device that relates to the rights, safety, or welfare of patients.

10.3 Adverse Event Reporting – Procedures for Investigators

The Principal Investigator and co-investigators will review any AEs and report any SAEs to the Sponsor as soon as possible and within 24 hours of obtaining knowledge of the event. The Principal Investigator and co-investigators will promptly report AEs to the Partner’s Institutional Review Board (IRB) and to the BU IRB (unless oversight is ceded by the BU IRB to the Partners IRB), in accordance with local requirements.

[name] is the Sponsor of the Investigational Device Exception for the BP and Zealand Pharma A/S is the Sponsor of the IND for ZP4207.

Reports of AEs will be submitted to the FDA in compliance with the terms of the Code of Federal Regulations.

All events meeting the definition of an AE must be collected and reported from the first trial-related activity from Visit 3 until the end of the post-treatment follow-up period. At each contact with the site (visit or telephone, excluding safety visits, where the patient is not seeing the Investigator or staff [e.g., visits to the laboratory], the patient must be asked about AEs. All AEs, either observed by the Investigator or reported by the patient, must be recorded by the Investigator and evaluated.

The Investigator should record the diagnosis, if possible. If no diagnosis can be made, the Investigator should record each sign and symptom as individual AEs.

Clinical Trial Protocol
ZP4207-16051

Version number: 3.0
Amendment 2.0
Date: 03 August 2016

All AEs must be recorded by the Investigator. One single AE Form must be used per AE from start to resolution. For SAEs, the SAE Form must also be completed.

AE information should include the following:

- Patient identification number on all pages
- Date and time of treatment start
- Date and time of onset and date of outcome
- Date and time of Investigator's first information on the (S)AE
- Seriousness
- Severity
- Causal relationship with IMP ZP4207
- Causal relationship with IMP insulin
- Causal relationship with IMP glucagon
- Causal relationship with medical device
- Causal relationship with procedures
- Interruption or withdrawal of treatment with IMP or medical device and other measures taken
- Outcome

All AEs are coded; details are described in the trial specific Data Management Plan.

The Investigator must report initial information in writing on the SAE Form for all SAEs to the Sponsor's responsible pharmacovigilance unit (here: Lindeq) immediately (within 24 hours) after obtaining knowledge about the event.

Name: [REDACTED]
Company: Lindeq
Address: [name]
Tel: [REDACTED]
Fax: [REDACTED]
Mobile: [REDACTED]
E-mail: [contact]

In addition and meeting the same timeline, Investigators must report all SAEs to Zealand Pharma A/S by forwarding the SAE Form electronically within 24 hours of obtaining knowledge of the event to the representatives of Zealand Pharma A/S.

Names: [REDACTED] and [REDACTED]
Address: [name]
Tel: [REDACTED]
E-mails: [REDACTED]

It is the responsibility of Lindeq to report all SUSARs that occur in this trial to the Competent Authorities and to the Investigators. It is the responsibility of the Investigators to report the SUSARs to the IRBs in accordance with the local requirements in force and the International Conference on Harmonisation (ICH) guideline for Good Clinical Practice (GCP). The trial monitor must be informed accordingly.

Clinical Trial Protocol
ZP4207-16051

Version number: 3.0
Amendment 2.0
Date: 03 August 2016

It is the responsibility of Lindeq to report all serious adverse reactions on insulin lispro and glucagon for injection to the Eli Lilly Pharmacovigilance department within 5 days.

It is the responsibility of the Investigators to report all UADEs to Beta Bionics within 24 hours of the time they are detected. It is the responsibility of the Investigators to report all UADEs to the IRB in accordance with the local requirements in force and the ICH GCP. It is the responsibility of Beta Bionics to report all UADEs to the Competent Authorities.

All device deficiencies should be documented and should be reported to Beta Bionics within 24 hours. Device deficiencies are inadequacies of a medical device with respect to its identity, quality, durability, reliability, safety, or performance.

Name: [REDACTED]
Company: Beta Bionics, Inc.
Address: [name]
[name], United States
Tel: [REDACTED]
E-mail: [REDACTED]

